13.2.6.2 Timed Function Tests

These tests provide additional measures of ambulatory capability in boys with DMD who can still walk. Commonly employed over many years [Brooke 1989, McDonald 1995], these tests are relevant to the disease in that they assess functional aspects of proximal muscle strength required for everyday ambulation. Timed function tests are substantially abnormal in boys with DMD compared to healthy boys [Beenakker 2005b]. Worsening values have been correlated with time to wheelchair dependency [Brooke 1989, McDonald 1995]. These tests can be sensitive to medical intervention; corticosteroid therapy has documented improvements in all 3 parameters [Mendell 1989, Griggs 1991, Beenakker 2005a]. Given their long-standing use and simplicity, there is substantial experience with the conduct of the tests and the analyses of the data and very high reproducibility has been demonstrated [Mayhew 2007].

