5.8 Secondary Variables

Subject [REDACTED] will be excluded from the As-Treated population in the analyses of all secondary endpoints.

5.8.1 6-Minute Walk Test

The distance walked at each visit and the change from baseline at each post baseline visit, as obtained from the 6-minute walk test (6MWT), will be summarized descriptively for ambulatory subjects with non-missing baseline 6MWT assessments. The distance walked at each will also be summarized for each actual age.

The endpoint will also be analyzed by means of a mixed model repeated measures (MMRM). An unstructured variance-covariance will be assumed and the estimation method will be the default, ReML. The model will include the factors for treatment, visit, age (6-11, 12-17, and ≥ 18 years), use of corticosteroids at baseline (yes vs no), and baseline 6MWD category (< 300 meters, ≥ 300 - < 400 meters, ≥ 400 meters), and baseline 6MWD as a covariate. Visit is considered as a categorical variable. From this analysis the mean change at each visit will be evaluated. If the model cannot converge, compound symmetry variance-covariance structure will be assumed.

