8.2 Matched Populations

To compare CINRG with Study 019, the matched populations are defined in the following table for different endpoints and analyses. Matching criteria will be adjusted if imbalance demographics and baseline characteristics are observed.

Endpoint/ Analysis	Age (Years) at Study Entry	Age (Years) at Assessment	Steroid Use	Ambulation status	Exclude EXON 51 and 45	Baseline value	Visit Year
Age at loss of ambulation	9-18	Not applicable	Cumulative Steroid use duration at study entry ≥ 12 months	Ambulatory at study entry	Yes	time taken to run/walk 10 meters 3.5-26.4 seconds ²	Not applicable
Age at FVC <1 liter	9-18	Not applicable	Not applicable	Non- ambulatory at study entry	Yes	1-3.08	Not applicable
Piece-wise regression based on FVC	Not applicable	≤ 22	Cumulative Steroid use duration at each assessment ≥ 24 months	Non- ambulatory at each assessment	Yes	Not applicable	≥ 2012
%- predicted FVC	9-21	Not applicable	Not applicable	Non- ambulatory at study entry	Yes	32.6- 110.3	Not applicable
%- predicted FEV1	9-21	Not applicable	Not applicable	Non- ambulatory at study entry	Yes	28.1- 104.0	Not applicable
PEF	9-21	Not applicable	Not applicable	Non- ambulatory at study entry	Yes	1.3-218.0	Not applicable
EK	9-18	Not applicable	Not applicable	Ambulatory at study entry	Yes	Score 0-15	Not applicable
6MWT	9-18	Not applicable	Cumulative Steroid use duration at study entry ≥ 12 months s	Ambulatory at study entry	Yes	36-553 meters	Not applicable
time taken to run/walk 10 meters	9-18	Not applicable	Cumulative Steroid use duration at study entry ≥ 12 months	Ambulatory at study entry	Yes	3.5-26.4 seconds	Not applicable
time taken to stand from supine	9-18	Not applicable	Cumulative Steroid use duration at study entry ≥ 12 months	Ambulatory at study entry	Yes	2.3-30 seconds	Not applicable
NSAA	9-18	Not applicable	Cumulative Steroid use duration at study entry ≥ 12 months s	Ambulatory at study entry	Yes	Total score 3-34	Not applicable

8.2.1 Analyses Based on Matched Populations of CINRG and Study 019

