Demographics and baseline characteristics (age, race, ambulation status, corticosteroid use (yes or no), duration of corticosteroid use, corticosteroid type, baseline 6MWD, baseline time to run/walk 10 meters, baseline time to stand from supine, baseline %-predicted FEV1, %-predicted FVC, PEF, EK score, NSAA total score) will be summarized descriptively for CINRG and Study 019 based on each matched population. The summary will be displayed by corticosteroid use (yes vs no) and cumulative steroid use (≥ 12 months vs < 12 months) for baseline ambulatory and non-ambulatory subjects separately. In general, the baseline is defined as the first visit in CINRG data. The baseline age in the FVC analysis using piece-wise regression models is the age at the first FVC assessments for both CINRG and Study 019.

The comparison to the natural history data (ie, CINRG data) based on matched subjects will be performed in FVC using piece-wise regression models, age to loss of ambulation, and age to FVC < 1 liter using Kaplan-Meier method.

Piece-wise regression models will be applied to log FVC in CINRG and Study 019 data, separately, using different ages as the changepoint. The most possible changepoint in terms of age will be chosen at the best model fit (ie, AICC value is the maximal). Scatter plots of log FVC and the most fitted piece-wise regression line will be generated for CINRG and Study 019, separately. Comparison between the observed and predicted FVC in Study 019 will be performed using repeated measures analysis of variance to account for within-subject correlation, where the predicted values are based on the regression equation estimated by the best fit regression model based on CINRG data.

The Kaplan-Meier method will be applied to the analysis of age to loss of ambulation and age to FVC < 1 liter. The median age to loss of ambulation and median age to FVC < 1 liter will be reported. The comparison between Study 019 and CINRG will be conducted via log-rank test by corticosteroid use at baseline (yes or no) and overall. The Kaplan-Meier curves will also be displayed.

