In Study 019, the loss of ambulation is defined as the disease progression reported as the adverse event or the time to run/walk 10 meters > 30 seconds, whichever occurs earlier. The event age is the one on the AE start date. The subjects who are ambulatory at the end of study will be censored on the last valid timed function tests assessment date. Age on that date will be used in the analysis. In the CINRG data, the age at the earliest report of the non-ambulation or the time to run/walk 10 meters > 30 seconds, whichever earlier, will be picked as the event age. If subjects in CINRG data do not report non-ambulation, the age at the last report of ambulation will be chosen as the censor age. A sensitivity analysis will be performing based on the loss of ambulation defined only by disease progression AE.

Similarly, the age at FVC < 1 liter is the one at the first time FVC < 1 liter. If subjects do not have FVC < 1 liter, the age at the last non-missing FVC assessment will be chosen as the censor age.

For CINRG data only, the observed values will be summarized descriptively for each actual age on 6MWT, time to run/walk 10 meters, time to stand from supine, NSAA total and linear scores, %-predicted FVC, %-predicted FEV1, PEF and EK total scores by corticosteroid use at baseline (yes or no) and overall based on the matched populations.

NSAA score derivation algorithms in Study 019 will be applied to CINRG data.

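### The two CINRG log-rank tests rest on wide inclusion ranges, do not adjust for baseline function, and have no stated rule for judging balance between the cohorts

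*SAP*

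**What the plan says.** SAP 8.2 tabulates a matched population for each endpoint. For age at loss of ambulation the criteria are age 9-18 at entry, ambulatory at entry, exclusion of exon 51 and 45, "Cumulative Steroid use duration at study entry ≥ 12 months", and "time taken to run/walk 10 meters 3.5-26.4 seconds". For age at FVC below 1 liter they are age 9-18, non-ambulatory at entry, the same exon exclusion, and a baseline value of 1-3.08. No unit is printed for that value; liters is the natural reading. All of these are inclusion rules. No pairing, caliper, propensity score or weighting is described.

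The one provision for imbalance is: "Matching criteria will be adjusted if imbalance demographics and baseline characteristics are observed". Under SAP 8.2.1 baseline characteristics "will be summarized descriptively for CINRG and Study 019 based on each matched population". The two age-at-event endpoints are then tested as follows: "The comparison between Study 019 and CINRG will be conducted via log-rank test by corticosteroid use at baseline (yes or no) and overall". In Study 019, loss of ambulation is a disease-progression adverse event or "the time to run/walk 10 meters > 30 seconds, whichever occurs earlier".

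Two other places bear on this. Protocol 13.2.6.2 says of timed function tests: "Worsening values have been correlated with time to wheelchair dependency". The within-study repeated-measures model for walk distance in SAP 5.8.1 includes a baseline category "and baseline 6MWD as a covariate".

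**The concern.** Restricting both cohorts to the same range trims the extremes but does not equalise the distributions inside it. A boy who covers 10 meters in 4 s and one who needs 25 s can both sit in the matched set, although the second is close to the event limit. If one cohort holds more of the faster boys, the log-rank test has no means of separating that from a drug effect.

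SAP 8.1 gives assessment of long-term treatment benefit as the purpose of the CINRG comparison, and these tests are two of the three formal comparisons in SAP 8.2.1; the third is the piece-wise FVC regression. The plan adjusts for baseline in the within-study model but not in the non-randomised comparison, where confounding is the main threat.

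The provision for imbalance does not close the gap. It does not say how imbalance is measured, what size triggers a change, or what the change would be. It also allows the populations to be redefined after the data have been seen, and it leaves the test unadjusted.

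**Working it through.** The plan states no alpha, power, effect size or event count for the CINRG comparison, so there is no figure of its own to reproduce. Steps 2 to 4 are illustrations on stated assumptions.

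**Step 1: width of the ranges (SAP 8.2).**
- 10-meter time: 26.4/3.5 = 7.54-fold, and log2(7.54) = 2.915 doublings. The upper end lies 30 − 26.4 = 3.6 s below the event limit. The range covers (26.4 − 3.5)/(30 − 3.5) = 22.9/26.5 = 86% of the span from 3.5 s to that limit.
- FVC: 3.08/1 = 3.08-fold, with the lower end at the event threshold itself.

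**Step 2: what the width allows.** The documents call timed function prognostic but give no hazard ratio. Assume each doubling of 10-meter time multiplies the hazard by h = 1.5, 2 or 3. Boys at the two ends of the range then differ in hazard by h^2.915 = 3.3, 7.5 or 24.6-fold. This shows how unlike two matched boys can be; it is not a measure of bias.

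**Step 3: a shift inside the range.** With cohort medians m1 and m2, the hazard ratio produced without any drug effect is roughly h^log2(m2/m1). For assumed medians of 7.4 and 9.1 s, log2(9.1/7.4) = 0.298, giving 1.13, 1.23 and 1.39. With equal medians it is 1.

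**Step 4: simulated false-positive rate, no drug effect.** The planned duration (240 × 7/365.25 = 4.6 years) and the 3.5-26.4 s range come from the documents. The assumptions are:
- 48 boys per cohort
- log2 standard deviation 0.75, truncated to the range
- entry age uniform on 9-15 years
- hazard 0.15 per year at 7 s
- follow-up 2.3 to 4.6 years, giving 41 to 50 events
- two-sided 5% level, 1000 runs per cell

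The log-rank is on age, as the SAP plans. The Cox model is on time since entry with log2 baseline time as covariate. Cells show h = 1.5 / 2 / 3.

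| Approximate medians (s) | Log-rank on age, % | Adjusted Cox, % |
|---|---|---|
| 7.4 v 7.4 | 4.3 / 5.0 / 5.2 | 5.0 / 4.8 / 5.2 |
| 7.4 v 8.3 | 5.9 / 6.1 / 6.3 | 5.5 / 5.7 / 5.2 |
| 7.4 v 9.1 | 6.5 / 8.5 / 13.7 | 4.3 / 5.6 / 4.3 |
| 7.4 v 10.0 | 7.5 / 11.9 / 21.9 | 4.5 / 4.8 / 4.7 |

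The simulation standard error at a true 5% is √(0.05 × 0.95/1000) = 0.7 percentage points. The second row is therefore not clearly above 5%, and 6.5% is only marginally so.

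FVC was not simulated. There the argument is structural: the baseline value is the same measurement that defines the event.

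**The case against.** **The populations are matched on more than one range.** This is true. Age, ambulation status and exon exclusions apply to both endpoints, and steroid duration to loss of ambulation. They narrow the cohorts, but none fixes function at a given age. Using age as the time scale does not fix it either: the inflation in step 4 arises on that scale. The split by steroid use adds little for loss of ambulation, where at least 12 months of use is already required.

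**The plan looks for imbalance and promises to act.** It does, and that deserves credit. What stands against it is the absence of a metric, threshold and method. The SAP 8.2.1 list of baseline variables also has %-predicted FVC but not FVC in liters, which is the matching variable for the FVC endpoint.

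**No imbalance is shown.** This stands in full. A reader might infer that the wide range itself biases the test, or that Study 019 boys are known to start better. The documents support neither: with equal distributions the log-rank holds its level, and no CINRG or Study 019 distributions are given.

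**The study is a safety study without a formal hypothesis, and CINRG is there to aid understanding.** SAP 1, 3.1 and 3.4 do say this, so it would be too strong to say that the trial's conclusion rests on these two tests. SAP 8.1 nevertheless uses the comparison to judge treatment benefit.

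**All Study 019 boys had earlier ataluren, so adjusting for baseline could remove earlier benefit.** This is a fair limit on interpretation, but the SAP already conditions on baseline function through its ranges.

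In addition, the 10-meter cell in the first row of the table ends in what looks like a footnote marker, with no note in the available text. Any qualification it carries is unknown.

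**Conclusion.** The concern holds as a gap in prespecification, not as a demonstrated bias. For age at loss of ambulation and age at FVC below 1 liter, the plan compares non-randomised cohorts that share inclusion ranges, without adjusting for a baseline value that both cohorts need for matching and with no working rule for balance.

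What this costs depends on facts that the documents do not give. Under the assumptions above, the false-positive rate is unaffected when the cohorts are balanced and barely affected when medians differ by under 1 s. At about 7.4 versus 9.1 s it is 6.5% to 13.7%, and at about 7.4 versus 10 s it is 7.5% to 21.9%. Adjustment keeps it near 5% throughout. The error would favour whichever cohort starts with better function, and that cohort is not known.

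The point is limited to these two tests. For the other functional endpoints SAP 8.2.1 plans only descriptive CINRG summaries, and the piece-wise FVC analysis uses no baseline range. The change should be made before the comparison is run.

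**What to change.** In SAP 8.2.1, before outcomes are compared, make the main analysis of these two endpoints a Cox model with cohort, age at entry, and either baseline 10-meter time on the log scale (loss of ambulation) or baseline FVC (FVC below 1 liter). State the time scale: age with delayed entry at study-entry age, or time since entry. Propensity or overlap weights on the same variables would be an acceptable alternative. Keep the log-rank tests as supportive.

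In SAP 8.2, replace the open-ended sentence on adjusting the criteria with a balance rule: standardized differences in each matched set, reported against a stated limit, with the action to take if the limit is exceeded. Add FVC in liters to the baseline summary and print the unit of the 1-3.08 range.

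The cost is SAP text and programming on variables that the matching already requires in both databases. There are two downsides. Proportional hazards has to be checked. And because every Study 019 boy had prior ataluren, the adjusted estimate describes benefit from study entry onward, which is also what matching on baseline ranges already implies.

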5.8.2 Timed Function Tests

Timed function test data (ie, time to stand from supine and time to run/walk 10 meters) and change from baseline to each post baseline visit will be summarized descriptively by visit for ambulatory subjects with non-missing baseline timed function tests assessments. Similarly the time to stand from supine and time to run/walk 10 meters will also be summarized for each actual age.

Timed function test (TFT) data imputation rules as the following will be used in the summary.

- If time to run/walk 10 meters > 30 sec, then set to 30 sec.
- If time to stand from supine > 30 sec, then set to 30 sec.

Similar to 6MWT, the time to stand from supine and time to run/walk 10 meters of will also be analyzed by means of a mixed model repeated measures (MMRM) where baseline is baseline time taken to stand from supine and time taken to run/walk 10 meters, respectively.

The Kaplan-Meier method will be applied to the analysis of age at loss of ambulation. The median age at loss of ambulation will be reported by corticosteroids use at baseline. The Kaplan-Meier curves will also be displayed. The age at loss of ambulation is defined as age of the disease progression reported as the adverse event or age at the time to run/walk 10 meters > 30 seconds, whichever occurs earlier. The subjects who are ambulatory at the end of study or discontinuation will be censored on the last valid timed function tests assessment date. Age on that date will be used in the analysis. A sensitivity analysis will be performing based on the loss of ambulation defined only by disease progression AE.

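### SAP 8.2.1 gives an event age for loss of ambulation only at the AE start date, so losses found first, or only, by the 10-meter test can be dated late or not at all in the comparison with CINRG

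*SAP*

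**What the plan says.** SAP 8.2.1 sets the Study 019 event as follows: "In Study 019, the loss of ambulation is defined as the disease progression reported as the adverse event or the time to run/walk 10 meters" above 30 seconds, taking the earlier. The next sentence fixes the age: "The event age is the one on the AE start date". It is not limited to AE-triggered losses, and 8.2.1 gives no other event-dating rule for Study 019.

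The same section then covers three related matters:
- Censoring: "The subjects who are ambulatory at the end of study will be censored on the last valid timed function tests assessment date".
- CINRG event age: "the age at the earliest report of the non-ambulation or the time to run/walk 10 meters > 30 seconds, whichever earlier, will be picked".
- Sensitivity: "A sensitivity analysis will be performing based on the loss of ambulation defined only by disease progression AE".

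SAP 5.8.2 analyses the same endpoint in Study 019 alone and dates it differently: the age of the progression AE or the "age at the time to run/walk 10 meters > 30 seconds, whichever occurs earlier".

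The cohorts are compared by log-rank test, by baseline corticosteroid use and overall (SAP 8.2.1). SAP 8.1 says the CINRG comparison is meant to assess long-term treatment benefit.

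**The concern.** The event definition has two triggers and the dating rule has one. Within 8.2.1 the rule does not fit the definition just before it. It also differs from 5.8.2 for the same boys, and from the rule for the cohort they are compared with. A programmer following 8.2.1 to the letter would date some Study 019 losses later than in 5.8.2 and would have to improvise for others.

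The date is the core derivation in a time-to-event comparison. CINRG losses carry no matching delay, so any error from the literal rule runs one way. In a single-arm, open-label study, this comparison with an external control is where a delay in loss of ambulation would be read as benefit.

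**Working it through.** **No planned figure to reproduce.** SAP 3.4 bases the sample size on eligibility, not on a hypothesis. No alpha, power or effect size is stated for this comparison.

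**Step 1: the rules side by side.** Let A be the age at the AE start and T the age at the first 10-meter time above 30 seconds.
- SAP 5.8.2: event age = min(A, T).
- SAP 8.2.1, literal: event age = A.
- CINRG: event age = min(first report of non-ambulation, T).

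For a boy with both dates, literal minus 5.8.2 = A − min(A, T) = max(0, A − T), which is never negative.

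| Boy (illustrative ages) | 5.8.2 | 8.2.1, literal |
|---|---|---|
| AE at 12.0, test at 12.6 | 12.0 | 12.0 |
| Test at 12.0, AE at 12.6 | 12.0 | 12.6 (0.6 years later) |
| Test at 12.0, no AE | 12.0 | none |

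The third boy is not censored either. The 8.2.1 censoring rule covers only those still ambulatory at the end of study, and the SAP treats a 10-meter time above 30 seconds as non-ambulatory (SAP 3.2).

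**Step 2: can test-first or test-only losses occur?** Two features of the protocol pull in opposite directions.
- Timed tests are 48 weeks apart (Protocol 7.2.17). AEs are collected at every 12-weekly visit (Protocol 7.2.24) with an onset date (Protocol 8.3). That is 48/12 = 4 AE visits per test interval, so the AE will often come first, and the two rules then agree.
- Nothing in the protocol makes a 10-meter time above 30 seconds reportable as an AE. Abnormal physiological tests qualify if they need intervention or further investigation (Protocol 8.1.1), and AEs are elicited by open-ended questions (Protocol 8.2). A failed test with a late AE, or none, is therefore possible.

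The documents give no count of either.

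**Step 3: illustrative size with no true difference.** All inputs are assumptions:
- 50 boys per cohort, entry age uniform from 9 to 14 years;
- follow-up 240/52 = 4.6 years;
- exponential time to loss with mean 4.6 years, so 1 − e⁻¹ = 63% have events;
- log-rank test on age at two-sided 5%, without entry-age adjustment, 1,000 runs per row;
- losses with no AE within follow-up treated as censored at its end.

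A false win is a significant result favouring Study 019 (nominal 2.5%).

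| Test-first | Test-only | AE delay (years) | Shift in Study 019 median (years) | False wins, earlier-of | False wins, literal |
|---|---|---|---|---|---|
| 0% | 0% | 0 | 0.00 | 2.4% | 2.4% |
| 10% | 0% | 0.25 | 0.03 | 3.0% | 3.0% |
| 20% | 5% | 0.5 | 0.37 | 1.4% | 5.4% |
| 30% | 10% | 0.5 | 0.74 | 1.9% | 10.6% |
| 30% | 20% | 0.9 | 1.43 | 2.3% | 32.9% |

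The simulation standard error at 2.5% is √(0.025 × 0.975/1000) = 0.5 percentage points.

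**Step 4: delay alone.** A second model isolates late AEs, with no test-only losses. It assumes 45 Study 019 and 60 CINRG boys, entry age 9 to 15, loss age about normal (mean 13.5, SD 2.5), 4.6 years of follow-up, a log-rank test allowing for entry age, and 600 runs. False wins under the earlier-of rule were about 1% to 3%. Under the literal rule they were:
- 10% test-first, 0.25 years: 3.8%;
- 20% test-first, 0.5 years: 3.8%;
- 50% test-first, 0.5 years: 7% to 8% over two sets of runs (median shift 0.25 years);
- 50% test-first, 0.9 years: 17% to 20% (median shift 0.46 years).

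Delay alone matters little unless the share is large. Test-only losses carry much of the larger effects in Step 3.

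**The case against.** The strongest reply is that the sentence says only which AE date to use when the AE is the trigger. Two things support this. The sentence before it takes the earlier trigger. And the AE-only sensitivity analysis would be nearly redundant if the main analysis already took every age from the AE. On that reading 5.8.2 supplies the missing date and no boy is misdated. This is a fair account of the probable intent, but 8.2.1 does not say it, and test-triggered losses still have no date there. The same edit is needed on either reading.

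A reader might go further and infer that the SAP prescribes the AE date even when the test came first, or that Study 019 ages will come out later. The documents support neither: the first is not written, and the second depends on unknown numbers of test-first and test-only boys.

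A reader might also quote much larger error rates. In the second model, making 30% or 50% of losses test-only and removing them as events gives about 30% or 70% false wins. The SAP does not say such boys are dropped or censored; it leaves their age unspecified. The 32.9% in Step 3 shares this weakness. The second model also allows for entry age, which the planned log-rank test is not stated to do.

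Finally, the comparison is supportive. The primary endpoint is safety, and age at loss of ambulation is not among the endpoints in SAP 3.3. That limits the weight of the point, not the need to settle the date.

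**Conclusion.** The point holds as a defect in the dating rule, with a known direction and an unknown size. Followed literally, 8.2.1 can only date Study 019 losses later than 5.8.2 does, or leave them undated, while CINRG keeps its earliest date. Any error therefore favours ataluren.

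Only test-first and test-only boys are affected, and the 12-weekly AE collection makes it likely that many boys are not. The simulated range runs from no visible effect to a large one. It rests wholly on assumed shares, delays and cohort sizes and, where test-only losses are included, on an assumed handling of them. It shows why the rule should be settled before analysis; it does not estimate the bias in this study.

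**What to change.** In SAP 8.2.1, replace the dating sentence with: *The event age is the age at the earlier of the AE start date and the date of the first valid 10-meter time >30 s.* This is the 5.8.2 rule with the test date made explicit. It gives every test-triggered loss an event age and matches the earlier-of-two-sources rule already used for CINRG. Keep the AE-only definition as the stated sensitivity analysis.

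The cost is one sentence of SAP text and the matching line in the derivation program. No new data are needed, because test dates and AE onset dates are already collected.
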